#### Exclusion Criteria

1. Advanced airway management prior to 1st dose administration

- 2. Known allergy to fentanyl, sufentanil, or meperidine
- 3. Known prisoner
- 4. Known pregnancy
- 5. ED pain treatment contraindicated
- 6. Estimated BMI >40
- 7. Significant respiratory depression
- 8. Known or suspected gastrointestinal obstruction, including paralytic ileus

Study Intervention: The study intervention will be the administration of 30 micrograms of DSUVIA in tablet form utilizing a sublingual applicator following informed consent for participation.

Study Intervention Arm: Patients randomized to the study intervention arm will receive DSUVIA via approved applicator as soon as feasible after randomization. A single dose of DSUVIA will be provided as directed on the package insert. Pre-randomization pain treatment will not be prohibited for study participation and dosage and narcotic type will be documented and recorded.

Standard Care Arm: Patients randomized to the standard care arm will receive standard care pain management. Dose administered and the respective narcotic will be recorded. Pre-randomization pain treatment will not be prohibited for study participation and dosage and narcotic type will be documented and recorded.

Randomization and Masking: Individual patients meeting all inclusion and no exclusion criteria in the emergency department will be randomized and assigned according to a 1:1 ratio of DSUVIA or standard care pain treatment using a permuted block design with variable block sizes of 4 and 6. A predefined randomization assignment will be utilized. The arm assignment will be provided in real time at the individual patient level. Trauma attending and ED physicians will not be masked to treatment assignment as the study intervention will not be blinded. Arm assignment will be concealed to all outcome assessors for follow up.

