#### Inclusion Criteria

- 1. Trauma activation (Level I, II or III)
- 2. Age 18-70 years inclusive.
- 3. Need for pain treatment based upon an NRS (0-100) clinical pain measurement  $\geq 50$
- 4. Estimated time in Emergency Department > 30 minutes following informed consent

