## IV. Outcomes

**Primary Outcome:** The primary outcome for the pilot trial will be the Verbally administered Numeric Rating Scale (VNRS) for clinical pain measurement (0-100) at 30 minutes following randomized medication administration. 

Secondary Outcomes: Secondary outcomes will include adverse events including hypoxia needing supplemental oxygen (SpO2 < 90%); hypotension (systolic blood pressure < 90mmHg); advanced airway or bag mask ventilation; incidence of nausea/vomiting/headache/dizziness requiring treatment; serial (30 minute intervals until ED discharge, up to 120 minutes or rescue narcotic administration) measurements of a) VNRS for clinical pain (0-100), b) Patient Global Assessment (PGA) of Pain Control, c) Richmond Agitation-Sedation Scale (RASS) scores, and d) time-weighted Summed Pain Intensity Difference (SPID); number of rescue narcotic doses at 30 minutes and during ED stay (up to 120 minutes); time to a reduction in VNRS pain score of 10 points; patient cognitive function as assessed by the Six Item Screener (SIS) at 30 minutes; Healthcare Professional Global Assessment (HPGA) of the method of pain control at 30 minutes; and acceptability of pain treatment to health care providers.

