#### **Time-weighted Summed Pain Intensity Difference (SPID) at 30-minute intervals:**

Time-weighted SPID measurements will be calculated at approximate 30-minute intervals until discharge from the ED (up to 120 minutes) or rescue narcotic administration, will be determined when feasible. Essentially, the SPID represents serial assessments of pain intensity over time, weighted by time differences. SPID will be calculated using values from a 101-point continuous pain intensity scale (0 = no pain to 100= worst pain imaginable). The Pain Intensity Difference (PID) (e.g., raw differences in pain intensity) is calculated by subtracting the pain intensity at each time point from the pain intensity at time 0. The SPID is then calculated by multiplying the PID score at each post dose time point by the duration (in hours) since the preceding time point and then summing the values over the relevant time period. If patients did not complete the full 120 minutes, the last pain observation was carried forward.

#### Number of rescue doses of narcotic at 30 minutes and until ED discharge (up to 120

**minutes):** The number of doses of standard care pain treatment given within 30 minutes following randomly assigned intervention and total until ED discharge (up to 120 minutes), when feasible.

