#### Time to reduction of VNRS pain score of 10 points (up to 120 minutes)

The time in minutes will be determined for the VNRS pain score (0-100) to be reduced by 10 points following randomized assignment administration for patients, when feasible.

Cognitive function at 30 minutes using Six Item Screener (SIS): The SIS will be used to detect cognitive impairment (e.g., sleepiness, confusion, memory impairment and reaction time)

at 30 minutes. Using a cutoff of  $\leq$  4 (out of 6) to reflect cognitive impairment has been proposed for ED use and has been used in prior studies of treatment of acute pain with sufentanil in the ED.

Healthcare Professional Global Assessment (HPGA) of the Method of Pain Control at 30 minutes: The HPGA of the method of pain control will also be reported by the healthcare professional (primarily nurses) at the 30-minute time period as the PGA above.

Acceptability to health care providers survey: An acceptability to health care providers score will be requested of health care providers in the ED including ED nurse, ED trauma team member and/or trauma surgery team member at 30 minutes or when feasible. The score (-2 to +2; 5-point scale) ratings will be from; very dissatisfied, dissatisfied, neither satisfied nor dissatisfied, satisfied, very satisfied, and will document providers assessment regarding the individual patient's pain management process, ease and acceptability relative to past experiences, when feasible.

Predefined Subgroups: Predefined subset analyses will be performed on: sex (male/female), Injury Severity Score (ISS  $< or \ge 16$ ), age ( $< or \ge 50$ ), blunt versus penetrating injury, history of pre-injury opioid use (Y/N), air versus ground prehospital transport, transport origin (scene versus outside ED).

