## V. Screening and Enrollment

Subjects will be identified prospectively in the ED by research personnel that are trained and familiar with the inclusion and exclusion criteria. Those patients who meet all inclusion and no exclusion criteria will be approached for informed consent, and once obtained, randomized to DSUVIA or standard care based upon the predetermined randomization assignment. Subjects will be paid \$25.00 in a Vincent Pay card upon completion of the study.

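### No VNRS is required between the qualifying score and study drug, so the baseline for SPID and the 10-point fall is undefined, and prior opioid is adjusted for only if it is found unbalanced

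*Combined protocol and SAP*

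**What the plan says.** All references are to the combined protocol and SAP.

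- **Eligibility.** Section III, Inclusion Criteria, item 3 reads "Need for pain treatment based upon an NRS (0-100) clinical pain measurement", with a threshold of 50. Neither this item nor the synopsis says when the score is taken, or whether it comes before or after earlier analgesia.
- **Earlier treatment.** Section III, under both the Study Intervention Arm and the Standard Care Arm: "Pre-randomization pain treatment will not be prohibited for study participation and dosage and narcotic type will be documented and recorded".
- **Order of steps.** Section V: "Those patients who meet all inclusion and no exclusion criteria will be approached for informed consent, and once obtained, randomized to DSUVIA" or to standard care. DSUVIA is then given "as soon as feasible after randomization" (section III). No section requires a VNRS at randomization or just before dosing.
- **Outcomes.** Section IV sets the primary VNRS "at 30 minutes following randomized medication administration". SPID is built by "subtracting the pain intensity at each time point from the pain intensity at time 0", and time 0 is not defined. For the 10-point fall, the clock runs from administration of the assigned treatment, but the score from which the 10 points are counted is not named.
- **Analysis.** Section VI tests Aim 1 with an unadjusted t-test. The adjusted models take site and whichever baseline characteristics turn out unbalanced. Neither baseline VNRS nor opioid given before randomization is named. The predefined opioid subgroup is use before the injury, which is a different variable.

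**The concern.** Consent, randomization and dosing all fall between the qualifying score and the first dose, and opioid may be given or take effect in that interval. The score that made a patient eligible may therefore not describe the patient at dosing. Three things follow.

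1. Two analysts following section IV could compute different SPID values and different 10-point events from the same patient, depending on which score each takes as baseline. With the qualifying score, relief obtained before study drug counts as response.
2. Patients already relieved may have less scope to show a treatment difference at 30 minutes, and opioid still taking effect adds variation to the primary outcome.
3. Two variables likely to predict the 30-minute score, pain just before dosing and opioid already on board, enter the model only if a balance check selects them. Precision is given up, and the content of the model depends on the data.

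**Working it through.** **1. SPID and the 10-point fall.** The documents give the SPID formula: the pain difference from time 0, multiplied by hours since the preceding point, then summed. The 30-minute schedule to 120 minutes gives four intervals of 0.5 h. The patient is hypothetical: qualifying score 70, score at dosing 40, no later change.

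- Time 0 = qualifying score: (70 − 40) × 0.5 × 4 = 60.
- Time 0 = pre-dose score: (40 − 40) × 0.5 × 4 = 0.

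In general the two versions differ by (qualifying score − pre-dose score) × 2 h. With 70 as reference, the first post-dose reading of 40 is already 30 points down, so the 10-point event is met at the first assessment. With 40 as reference it is never met. The offset arises before study drug, so it falls on both arms alike in expectation.

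**2. The plan's own power.** Inputs from section VI, Sample Size: effect size d = 0.45, 75 per arm, two-sided alpha 0.05, stated power 80%.

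Power = Φ(d × √(n/2) − 1.96) = Φ(0.45 × √37.5 − 1.96) = Φ(2.756 − 1.96) = Φ(0.796) = 78.7%.

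This is close to the stated 80%, and any illustration should start from 78.7%. With SD 21, d = 0.45 is 0.45 × 21 = 9.45 points. The plan's 7.1 points does not match that product, but this is a separate matter and nothing here depends on it.

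**3. Dilution (assumption only).** The documents give no share of patients relieved by dosing. Let f be that share and k the fraction of the planned effect they keep, so d = 0.45 × (1 − f × (1 − k)).

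| f | d, k = 0.5 | Power | d, k = 0 | Power |
|---|---|---|---|---|
| 0 | 0.450 | 78.7% | 0.450 | 78.7% |
| 10% | 0.428 | 74.5% | 0.405 | 69.9% |
| 20% | 0.405 | 69.9% | 0.360 | 59.7% |
| 30% | 0.383 | 64.9% | 0.315 | 48.8% |

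**4. Noise in the 30-minute score (assumption only).** Suppose a share f of both arms carries a further fall of c points from earlier opioid. Then SD = √(21² + f(1 − f)c²).

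- f = 20%, c = 10: SD = √(441 + 16) = 21.4, power at 9.45 points 77.2%.
- f = 50%, c = 20: SD = √(441 + 100) = 23.3, power 70.1%.

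**5. Chance imbalance (same assumptions).** The 95% limit on the shift in the unadjusted difference is 1.96 × √(f(1 − f) × 2/75) × c.

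- f = 20%, c = 10: 1.96 × 0.065 × 10 = 1.3 points.
- f = 50%, c = 20: 1.96 × 0.082 × 20 = 3.2 points.

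**The case against.** The strongest reply is that the plan is tighter than it looks. Section III says "Individual patients meeting all inclusion and no exclusion criteria in the emergency department will be randomized", which can be read as requiring the score to hold at randomization. Criterion 3 speaks of a need for treatment, not only a number. Because criteria are met in the ED, prehospital opioid will often precede the score. The 10-point clock starts at study drug, and SPID is summed over post-dose points, so dosing is the natural origin. Prior opioid precedes randomization and is balanced in expectation. Opioid type and dose are recorded, and section VI plans review of prehospital and ED records.

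Much of this stands, and it rules out several stronger readings that a reader might infer.

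- *A patient whose score has dropped to 35 by randomization is plainly still eligible.* The text does not settle this either way. The clear exposure is narrower: opioid given in the ED between score and dosing, or earlier opioid still taking effect.
- *A 10-point fall can be completed before any study drug.* The clock does not allow that. Only the reference score is open.
- *One arm is favoured.* Treatment before randomization gives no systematic advantage to either arm.
- *Aim 2 events on study drug alone cannot be separated from those on top of earlier opioid.* A yes/no tabulation can be made from data already planned.
- *A stated loss of power has been shown.* It has not. A patient at 35 still has 35 points of room against a planned 9.45.

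The reply does not supply a pre-dose score, a definition of time 0, a reference score for the 10-point fall, or a named covariate. A natural reading of time 0 as dosing still lacks a required measurement at that moment.

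**Conclusion.** The concern holds as a gap in baseline definition and covariate specification. The ambiguity in SPID and the 10-point fall follows from the text and needs no assumption about frequency: the same patient can score 60 or 0. The consequences for the treatment comparison are noise, dilution and chance imbalance at 75 per arm, without systematic bias between arms.

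Their size cannot be derived from the documents. The figures in steps 3 to 5 of the working rest on assumed shares and assumed carry-over, and show only what would follow if those held.

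A reader might also infer that entry should be restricted to patients still at 50 or above after any earlier analgesic. The documents do not require that conclusion. It is a choice of population, and if 10-30% of candidates were relieved beforehand it could exclude that many.

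**What to change.** 1. In section IV, require a VNRS immediately before the assigned medication in both arms. Define it as time 0 for SPID and as the reference for the 10-point fall.
2. In section VI, name that score and pre-randomization opioid (yes/no) as covariates in the adjusted Aim 1 model, whether or not they are balanced. Name pre-randomization opioid likewise in the Aim 2 and Aim 3 models where event counts allow.
3. Tabulate Aim 2 events by pre-randomization opioid.
4. The sponsor should reconcile criterion 3 with the pre-randomization treatment text on when the qualifying score is taken. No eligibility or treatment rule is proposed here.

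The cost is one extra verbal score per patient and slightly larger models. The opioid indicator uses data already recorded, and items 1 to 3 exclude nobody. There are two limits. A yes/no indicator ignores dose and timing, which the pre-dose score reflects only in part. And because the trial is open label, a score taken after the assignment is known could be influenced by it, so it should follow the same procedure in both arms.

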## III. Study Design/Setting

The current proposed study will be a 3-year, multi-center, open label, randomized trial utilizing 2-4 level-1 trauma centers from within the LITES network and will enroll approximately 150 patients. The University of Pittsburgh will be the Clinical Coordinating Center and the Data Coordinating Center for the study.

Study Population: Blunt or penetrating injured patients who require pain management in the Emergency Department phase of care.

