#### Secondary Outcome Definitions:

**Hypoxia, hypotension or need for advanced airway:** The principal safety outcome for the trial will be the incidence of serious adverse events following the first dose of analgesic following randomization including hypoxia (SpO2 < 90%), hypotension (SBP < 90 mmHg) or the need for advanced airway management (placement of an endotracheal tube, supraglottic airway or bag mask ventilation) until ED discharge (up to 120 minutes), when feasible.

Composite outcome of nausea, vomiting, headache, and/or dizziness requiring treatment: The incidence of nausea, vomiting, headache, and/or dizziness requiring treatment will be recorded for initial 30 minutes, when feasible.

Verbally administered Numeric Rating Scale (VNRS) pain measurements (0-100) at 30- minute intervals: VNRS for clinical pain (0-100) measurements at approximate 30-minute intervals until discharge from the ED (up to 120 minutes) or rescue narcotic administration, will be obtained when feasible.

**Patient Global Assessment (PGA) of Pain Control at 30-minute intervals:** The PGA of the method of pain control at approximate 30-minute intervals until discharge from the ED (up to 120 minutes) or rescue narcotic administration, will be obtained when feasible. The research team will read the following statement aloud to the subject and the response will be recorded: "Overall, would you rate this method of pain control during the last 30 minutes/hours as being poor (1), fair (2), good (3), or excellent (4)?"

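### The plan says arm is concealed from outcome assessors for follow-up, but the primary and most secondary outcomes are rated or decided in an open-label ED where no masking is described

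*Combined protocol and SAP*

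**What the plan says.** Section III calls the study a "multi-center, open label, randomized trial utilizing 2-4 level-1 trauma centers". The Randomization and Masking paragraph in that section says "Trauma attending and ED physicians will not be masked to treatment assignment as the study intervention will not be blinded". Its next sentence is "Arm assignment will be concealed to all outcome assessors for follow up". The plan does not say who these assessors are, what follow-up means, or how concealment would be kept.

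The intervention is 30 micrograms of "DSUVIA in tablet form utilizing a sublingual applicator following informed consent for participation". The comparator is standard care, and no dummy is described.

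Section IV makes the primary outcome the verbal 0-100 pain score (VNRS) 30 minutes after the randomized medication. Its secondary outcomes run to ED discharge, with a cap of 120 minutes. For the Patient Global Assessment (PGA), "The research team will read the following statement aloud to the subject and the response will be recorded". The Healthcare Professional Global Assessment (HPGA) "will also be reported by the healthcare professional (primarily nurses) at the 30-minute time period". The acceptability survey goes to the ED nurse, an ED trauma team member and/or a trauma surgery team member.

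Under Section V, research personnel find patients in the ED. Those patients are then "approached for informed consent, and once obtained, randomized to DSUVIA or standard care".

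**The concern.** The masking sentence gives an assurance that the rest of the design does not appear to support. In an open-label comparison of a sublingual tablet with usual care, a subjective pain score can move with what the patient expects of the treatment, whatever its true effect. A reader who takes the sentence at face value could treat the primary result, and the ratings under Aims 3 and 4, as protected from that influence. What is at stake is what the trial may claim about bias in its main outcome.

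**Working it through.** The plan gives no figure on masking to reproduce. The check is to ask, outcome by outcome, who determines the value and whether anything in the plan masks that person.

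| Outcome (Section IV) | Determined by | Masking described |
|---|---|---|
| Primary: VNRS at 30 minutes | Patient | None |
| Serial VNRS | Patient | None |
| SPID | Calculated from the patient's scores | None |
| Time to a 10-point fall | Calculated from the patient's scores | None |
| PGA | Patient, asked by the research team | None |
| HPGA | Healthcare professional, mainly nurses | None |
| Acceptability survey | ED nurse, ED trauma team, trauma surgery team | None; can include the physicians stated to be unmasked |
| Rescue narcotic doses | Treatment decision in the ED | None |
| Nausea, vomiting, headache or dizziness that needed treatment | Treatment decision in the ED | None |
| RASS | Rater not named | Not stated |
| Six Item Screener | Examiner not named | Not stated |
| Hypoxia, hypotension, advanced airway | Numerical thresholds or recorded events | Not stated; masked abstraction possible |

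**Count.** Patient-rated or derived secondary outcomes 4, clinician-rated 2, dependent on treatment decisions 2: 4 + 2 + 2 = 8 of 11, plus the primary outcome. Three secondary outcomes remain: RASS, the Six Item Screener, and the hypoxia, hypotension and airway outcome.

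**Two readings of the sentence.**

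1. If it covers the listed outcomes, it conflicts with the open-label design for the primary and those 8. Background (Section II) describes the numeric rating scale as self-reported, so masking the person who asks the question would not mask the rating.
2. If it covers only later follow-up, it reaches almost nothing listed, because no outcome extends past 120 minutes. The data elements in Section VI that run past the ED stay are ICU days and length of stay, and neither is a listed outcome.

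**Illustration of the underlying risk.** SD 21, 75 per arm and two-sided alpha 0.05 come from the Sample Size paragraph of Section VI. The shift is assumed, because the documents give no size or direction. The true effect is set to zero, and one t-test is used, ignoring the planned interim look.

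- Standard error of the difference = 21 × √(2/75) = 3.43.
- Noncentrality = shift / 3.43, with 148 degrees of freedom.
- False-positive rate = probability that a noncentral t falls outside the central t critical values.

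| Assumed shift (points) | Noncentrality | False-positive rate |
|---|---|---|
| 0 | 0 | 5.0% |
| 2 | 0.58 | 8.9% |
| 3 | 0.87 | 14.0% |
| 4 | 1.17 | 21.2% |
| 5 | 1.46 | 30.5% |

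The test is two-sided, so the rates are the same whichever arm the shift favours.

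**The case against.** The strongest reply is that the sentence is limited to follow-up and never promises masking of the 30-minute score. Section III says openly that the trial is open label and the intervention unblinded, so a report calling the pain score blinded would contradict the protocol. This has weight: the limiting words must be kept when the sentence is read, and open label is a legitimate choice. But it leaves a sentence about all outcome assessors that protects little or nothing on the outcome list, so correction is still needed.

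Three further points stand in part.

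- **Who collects the data.** A reader might infer that the staff who enrol patients also take the scores. The documents do not say so. They name research personnel for identifying patients and the research team for the PGA question, and they do not say who asks the VNRS or rates RASS. Only trauma attending and ED physicians are stated to be unmasked. That patients and nurses know the arm is a strong inference from a visible tablet with no dummy, but it is not stated. The wording of the PGA and HPGA does not settle it, since a rater can judge a method of pain control without being told the arm.
- **Whether the sentence applies to nothing at all.** A reader might conclude that it does. That goes too far. Saturation, blood pressure and airway events could be abstracted from records without arm information, and a separate masked rater for RASS or the Six Item Screener is not excluded.
- **What the error rates measure.** They describe open-label self-report and would be unchanged if the sentence were deleted. This is correct.

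**Conclusion.** The point holds. The stated concealment does not exist for the primary outcome and 8 of the 11 secondary outcomes. At most it could cover the objective safety items, if abstracted without arm information, or an unnamed RASS or Six Item Screener rater. For the primary outcome this rests on two facts in the documents: the patient gives the score, and no masking of the patient is described. It does not depend on who asks the question.

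The range of about 9% to 30% is conditional on an assumed shift of 2 to 5 points. A reader might infer that such a shift is to be expected, that it rivals the difference the trial is sized to detect, or that it favours DSUVIA. The documents support none of these. Nor is the open-label design itself the error. The defect is an assurance the design does not supply; it should be corrected, but it does not invalidate the planned comparison.

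**What to change.** 1. Delete the concealment sentence, or limit it to named items that are assessed or abstracted without arm information, and say how that is done.
2. State that these outcomes are unmasked: primary and serial VNRS, SPID, time to a 10-point fall, PGA, HPGA, acceptability, rescue doses, and nausea, vomiting, headache or dizziness that needed treatment. State that Aims 1, 3 and 4, and the treatment-dependent part of Aim 2, are interpreted on that basis.
3. Have the VNRS question read verbatim from a neutral script that names no treatment. The PGA question is already read from fixed wording. A script limits interviewer influence but does not mask the patient.

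The cost is protocol wording and a one-line script, with no extra staff or patients. The downside is that the plan's stated protection against bias becomes less favourable.
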